### 10.4.1 Haematological

Full blood count (FBC) should be performed at least every 2 weeks after the start of each course of chemotherapy.

Before each course:

WBC  $< 2 \times 10^9/L$  or Delay chemotherapy for at least

**Neutrophils**  $< 0.5 \times 10^9/L$  or one week.

Platelets  $< 100 \times 10^9/L$ 

Platelet/WBC recovery
delays therapy > 2 weeks
Omit CCNU for next course
and Reduce CCNU to 50 mg/m^2

in all subsequent courses.

**If further episode** Omit CCNU for next and all subsequent

courses (give full dose cisplatin).

**Nadir after course:** 

WBC  $< 0.5 \times 10^9 / L$  or Reduce CCNU to 50 mg/m^2

**Neutrophils**  $< 0.05 \times 10^9/L$  in the next and all subsequent

courses.

and after episode of neutropaenic fever

**If further episode** Reduce cisplatin to 50 mg/m^2

(with or without G-CSF administration) in the next and all subsequent

courses.

Platelets  $< 30 \times 10^9 / L$  Reduce CCNU to  $50 \text{ mg/m}^2$ 

in the next and all subsequent

courses.

**If further episode** Omit CCNU for next and all

subsequent courses (give full dose

cisplatin).

10.4.2 Neurotoxicity of vincristine

**Epileptic seizure** or Stop VCR in this course and

**Ileus** reduce VCR to 1 mg/m^2

in the next course

After recovery Give VCR at 100% doses

Significant dysaesthesia, muscular weakness Omit VCR until recovery

or abdominal pain

After recovery Give VCR at 100% doses

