## **Chemotherapy** 8 Cycles given at 6 weekly intervals

V – Vincristine 1.5 mg/m^2 (maximum 2 mg)

C – Lomustine (CCNU) 75 mg/m^2

P - Cisplatin 70 mg/m^2

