# 8.9 Chemotherapy during the radiotherapy phase

- All patients receive chemotherapy during irradiation.
- A total of 8 doses of vincristine will be administered.
- The first will be given during the first week of RT.
- Treatment with weekly vincristine will thus usually extend beyond the end of radiotherapy.
- Weekly administration of vincristine will be suspended for breaks in radiotherapy due to
  myelosuppression or other reason and will recommence when radiotherapy is restarted. In this
  case, eight doses of vincristine will still be given unless toxicity due to vincristine necessitates
  omission of this drug.

Vincristine 1.5 mg/m^2 (maximum dose 2 mg).

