### **Dose modification of vincristine:**

Epileptic seizure or Stop VCR in this course and reduce VCR to 1 mg/m^2

reduce VCR to 1 mg/m^2 in the next course

Omit VCR until recovery

After recovery Give VCR at 100% doses

Significant dysaesthesia, muscular weakness

or abdominal pain

After recovery Give VCR at 100% doses

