# 10. MAINTENANCE CHEMOTHERAPY

# 10.1 Summary of the regimen

Maintenance-chemotherapy starts 6 weeks after the end of radiotherapy.

Each course consists of:

- Cisplatin 70 mg/m^2 intravenously (6 hour infusion) day 1
- CCNU (Lomustine) 75 mg/ m^2 orally day 1
- Vincristine 1.5 mg/m^2 intravenously (bolus; max. dose 2 mg) day 1, 8 and 15

See section 10.3 and Appendices H and J for details of administration

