### 12. SERIOUS ADVERSE EVENTS AND TOXICITY REPORTING.

## Common Toxicity criteria definitions will be used for toxicity reporting.

The CTC (Appendix L) used in completion of the data forms will be the same for all participating groups.

Definition of serious adverse events (SAEs) is based upon the ICH GCP Guidelines

In this study, a serious SAE is defined as:

Any unexpected medical occurrence that:

- Results in death (death from tumour progression is not an SAE)
- Is life-threatening
- Requires unexpected inpatient hospitalisation or prolongation of existing hospitalisation
- Results in persistent or significant disability/incapacity
- Overdose that leads to symptomatic disease

In addition, for this study the following toxicities will also be defined as SAEs:

- Any grade 3 or grade 4 central neurotoxicity
- Any grade 3 or grade 4 unexpected toxicity

Ototoxicity as a result of cisplatin chemotherapy and radiotherapy to the cochlea is an expected complication of the treatment described in this protocol. As such, ototoxicity, including Grade 3 or 4 ototoxicity, is not regarded as a SAE in this study. The occurrence of ototoxicity will however be carefully monitored and stopping rules are in place for excessive ototoxicity (section 13.7).

Serious adverse events must be reported within 24 hours of the knowledge of the event by fax to the National Centre which will notify both the National Study Co-ordinator and the International Data Centre.

The International Data Centre will be responsible for informing the independent Data Monitoring and Safety Committee and other regulatory bodies as appropriate.

In addition, each National Data Centre will be responsible for informing their appropriate national regulatory bodies as appropriate.

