#### Rare

- Leucopaenia, Thrombocytopaenia, Anaemia
- Nausea and vomiting
- Raised LFTs (mild and transient)
- Convulsions
- Diplopia and Photophobia

Toxicity related to individual and cumulative dose of Vincristine

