Cortical	None	Mild somnolence or agitation, not interfering with function	Moderate somnolence or agitation interfering with function, but not with activities of daily living	Severe somnolence, agitation, confusion, disorientation or hallucinations	Coma, seizures, toxic psychosis		
Ataxia (incoordination)	None	Asymptomatic but abnormal on physical exam, not interfering with function	Mild symptoms interfering with function, but not interfering with activities of daily living	Moderate symptoms interfering with activities of daily living	Bedridden or disabling		
Confusion	Normal	Confusion or disorientation or attention deficit of brief duration; resolves spontaneously with no sequelae	Confusion or disorientation or attention deficit interfering with function, but not interfering with activities of daily living	Confusion or delirium interfering with activities of daily living	Harmful to others or self; requiring hospitalization		
Irritability (children <3 years of age)	Normal	Mild; easily consolable	Moderate; requiring increased attention	Severe; inconsolable	-		
Leukoencephalopathy associated radiological findings	None	Mild increase in SAS (subarachnoid space) and/or mild ventriculomegaly; and/or small (+/- multiple) focal T2 hyperintensities, involving periventricular white matter or <1/3 of susceptible areas of cerebrum	Moderate increase in SAS; and/or moderate ventriculomegaly; and/or focal T2 hyperintensities extending into centrum ovale; or involving 1/3 to 2/3 of susceptible areas of cerebrum	Severe increase in SAS; severe ventriculomegaly; near total white matter T2 hyperintensities or diffuse low attenuation (CT); focal white matter necrosis (cystic)	Severe increase in SAS; severe ventriculomegaly; diffuse low attenuation with calcification (CT); diffuse white matter necrosis (MRI)		
Seizure(s)	None	-	Seizure(s) self-limited and consciousness is preserved	Seizure(s) in which consciousness is altered	Seizures of any type which are prolonged, repetitive, or difficult to control (e.g., status epilepticus, intractable epilepsy)		
Mood	No change	Mild anxiety or depression	Moderate anxiety or depression interfering with function, but not interfering with activities of daily living	Severe anxiety or depression interfering with activities of daily living	Suicidal ideation or danger to self.		

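### The vincristine step-down after seizure or ileus ignores the 2 mg cap on the full dose, so the cut shrinks above 1.33 m² and is nil at 2.0 m²

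*Protocol*

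**What the plan says.** The full dose and its ceiling appear three times in the Protocol: in the chemotherapy box of the flow diagram in section 1.3, "Vincristine 1.5 mg/m 2 (maximum 2 mg"; in section 8.9 for the radiotherapy phase, "Vincristine 1.5 mg/m 2 (maximum dose 2 mg"; and in section 10.1 for maintenance, where the 1.5 mg/m² dose is given "intravenously (bolus; max. dose 2 mg) day 1, 8 and 15".

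For seizure or ileus, section 10.4.2 stops vincristine in the current course and then says "reduce VCR to 1 mg/m 2" for the following course, with a return to 100% after recovery. The dose-modification table in section 8.9 gives the same step, "reduce VCR to 1 mg/m 2 in the next course". That table's layout is broken in the available text, so section 10.4.2 carries the point.

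Neither rule gives a maximum in mg, a percentage, or a link to the dose the patient was actually receiving. No other section supplies one.

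**The concern.** A per-m² step-down works as a reduction only if the full dose also scales with body surface. Here it stops scaling at the ceiling, so the two doses converge as patients get larger. At 2.0 m² a patient who had a seizure on 2 mg is re-treated with 2 mg.

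The protocol itself says why an unchanged dose is a problem. Its vincristine monograph in Appendix I states: "Toxicity related to individual and cumulative dose of Vincristine". One of the two triggers is also serious under the protocol's own rules. Appendix L grades "Seizure(s) in which consciousness is altered" as III, and section 12 lists "Any grade 3 or grade 4 central neurotoxicity" as a serious adverse event.

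Large patients are in scope: section 5.1 admits patients up to just under 22 years.

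**Working it through.** **Inputs.** Full dose 1.5 mg/m², maximum 2 mg (sections 1.3, 8.9, 10.1). Step-down 1 mg/m² (sections 10.4.2, 8.9). Three doses per maintenance course and eight courses (section 10.1). Eight weekly doses with radiotherapy (section 8.9). The protocol states no percentage reduction, so there is no figure of its own to reproduce.

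**Formulas**, with B = body surface in m²:
- Full dose = min(1.5 × B, 2 mg). The ceiling binds at B = 2/1.5 = 1.33.
- Step-down as written = 1.0 × B. It reaches 2 mg at B = 2.0.
- Reduction = 1 − step-down/full.
- Proposed dose = 2/3 × full = min(1.0 × B, 1.33 mg).

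| B (m²) | Full (mg) | Step-down as written (mg) | Reduction | Proposed (mg) |
|---|---|---|---|---|
| 1.00 | 1.50 | 1.00 | 33% | 1.00 |
| 1.33 | 2.00 | 1.33 | 33% | 1.33 |
| 1.40 | 2.00 | 1.40 | 30% | 1.33 |
| 1.50 | 2.00 | 1.50 | 25% | 1.33 |
| 1.60 | 2.00 | 1.60 | 20% | 1.33 |
| 1.70 | 2.00 | 1.70 | 15% | 1.33 |
| 1.80 | 2.00 | 1.80 | 10% | 1.33 |
| 1.90 | 2.00 | 1.90 | 5% | 1.33 |
| 2.00 | 2.00 | 2.00 | 0% | 1.33 |
| 2.10, ceiling carried over | 2.00 | 2.00 | 0% | 1.33 |
| 2.10, no ceiling on step-down | 2.00 | 2.10 | 5% increase | 1.33 |

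**Per maintenance course (three doses).** From 1.33 m² the full course is 3 × 2 = 6.0 mg. The step-down course as written is 4.5 mg at 1.5 m², 5.4 mg at 1.8 m² and 6.0 mg at 2.0 m². The proposed course is 4.0 mg at all these sizes, so it removes a further 0.5, 1.4 and 2.0 mg respectively.

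**Share of planned treatment.** For a patient at the ceiling, 8 × 2 + 8 × 3 × 2 = 16 + 48 = 64 mg. The largest further loss is 2.0/64 = 3.1%.

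**Dose per m².** The capped full dose is already 2/1.5 = 1.33 mg/m² at 1.5 m², 2/1.8 = 1.11 at 1.8 m² and 2/2.0 = 1.00 at 2.0 m². The proposed dose gives 1.33/1.5 = 0.89, 1.33/1.8 = 0.74 and 1.33/2.0 = 0.67.

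**Comparison with the other numeric step-downs (section 10.4.1).** Neither drug has a ceiling. CCNU goes from 75 to 50 mg/m², nominally 1 − 50/75 = 33%. Cisplatin goes from 70 to 50 mg/m², nominally 1 − 50/70 = 29%. Appendix J rounds CCNU to 10 mg, including for reductions, so the delivered cut varies: 100 to 70 mg (30%) at 1.40 m², 80 to 50 mg (37.5%) at 1.00 m², 40 to 30 mg (25%) at 0.55 m². Each of these cuts still lowers the dose.

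**The case against.** The best defence is that 1 mg/m² is a target exposure, not a proportional cut: everyone comes down to the same per-m² dose for one course, and the ceiling has already brought large patients close to it. On that reading a patient between 1.33 and 1.9 m² still gets a real, if smaller, reduction. This part stands. A reader might infer that the protocol promises a one-third cut and breaks that promise for everyone above 1.33 m². The text does not support that: it states no percentage, and one-third is only what 1.5 to 1 mg/m² implies below the ceiling. Nor do the other rules deliver a constant percentage, as CCNU rounding shows. What the defence cannot rescue is 2.0 m² and above, where the event occurred at or below 1 mg/m² and the rule removes nothing.

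The second objection is practical reach, and most of it stands:
- The monograph lists convulsions as rare and paralytic ileus as occasional.
- Vincristine is stopped in the event course at every body size.
- Section 10.4 preserves individual clinical responsibility and offers advice from the study chairman, and the monograph accepts in general terms that unacceptable toxicity may require a lower dose. None of these supplies a dose, so they limit the harm without repairing the rule.
- Appendix J reaches 2.0 m², but it is a lomustine dosing table and does not show that patients of that size were enrolled.
- This version is dated July 2010. Section 13.1 planned recruitment to 31.12.2005 with possible prolongation, section 4.7.3.1 already cites a 2010 report on event-free survival, and Appendix M describes all UK children at this stage as at least 10 years old. Treatment may be complete or nearly so.

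Third, a tighter maximum puts large patients below the 1.0 mg/m² a small child receives after the same event, and the monograph says adult experience does not support even the 2 mg limit. This is a fair caution about the chosen value. It does not justify a step-down that leaves the dose unchanged.

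**Conclusion.** The point holds as a minor safety correction. The finding at 2.0 m² and above depends on no assumed percentage: with the ceiling carried over the rule changes nothing, and without it the dose rises. Between 1.33 and 2.0 m² the rule does reduce the dose, by a shrinking amount; whether that falls short depends on an intended proportional cut, which is an inference.

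The documents give no body-surface distribution and no numerical event rates, so the number of patients affected cannot be estimated; it is likely to be very small. A reader might also infer a threat to the trial's result. Nothing supports that: the rule is identical in both arms and does not bear on the event-free survival comparison or the power calculation.

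**What to change.** In sections 10.4.2 and 8.9, add a maximum so that the reduced dose is always below the dose at which the event occurred, for example 1 mg/m² with a maximum of 1.33 mg. This equals two-thirds of the full dose at every body size. The study committee should confirm the value, because two-thirds is inferred and the monograph lends no support to a tighter ceiling.

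The cost is one phrase in two places, by amendment, with no new data or visits. The clinical price is the further loss of vincristine in one maintenance course shown in the working, and the lower per-m² dose for large patients in that course.

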# 10.4.3 Nephrotoxicity

- > Nephrotoxicity is a major toxicity of cisplatin. Both glomerular and tubular toxicity must be monitored during treatment with cisplatin.
- > Dose modification is based on glomerular toxicity i.e. a reduction in Glomerular Filtration Rate (GFR).
- ➤ In the context of a multicentre international trial, it is appreciated that different national groups and individual centres have varying but well-established methods of measuring or estimating GFR. These include methods based on blood clearance of radioisotope e.g. MAG3 and clearance of Cr EDTA or Tc99m DTPA, estimation of creatinine clearance from the plasma creatinine level (e.g. using the Schwartz formula Appendix K) or by direct measurement of urinary creatinine clearance.
- > Any well established method of estimating GFR as detailed above may be used prior to chemotherapy.
- ➤ The estimation of GFR must be performed before the first course and at least before every other course (i.e. before courses 1, 3, 5, and 7).

Serum creatinine > 1.2 mg/dL (100μM) or higher than 1.5 x normal upper limit or Delay chemotherapy for 1 week GFR/Creatinine clearance < 80 ml/min per 1.73 m^2

**If no recovery**Perform estimation of GFR by clearance of radioisotope

Isotope GFR  $\geq$  60 and < 80 ml/min per 1.73 m^2 Use carboplatin 400 mg/m^2 instead of cisplatin for next course.

Perform estimation of GFR by clearance of radioisotope before next course

**Isotope GFR < 60 ml/min per 1.73m^2**Omit any platinum for next course.

Perform estimation of GFR by clearance of radioisotope before next course

# 10.4.4 Ototoxicity:

The Ototoxicity Grading System in PNET 4 is that used in the HIT 91 and HIT 2000 studies, as follows:

Grade 0: normal

Grade 1: ≤ 15 dB at ≤ 2000 Hz

Grade 2: 16-30 dB at ≤ 2000 Hz

Grade 3: 31-60 dB at ≤ 2000 Hz

Grade 4: >60 dB at ≤ 2000 Hz

It is, however, mandatory, for patients to have a Pure Tone Audiogram performed at the end of treatment. This audiogram will be either sent to the National Data centre or the grading recorded on the data forms and be graded according to both the HIT and Brock/CTC grading systems (Appendix L) to enable a comparion of ototoxicity between different treatment studies.

The Dose Modification of cisplatin is based on the sytem used in the HIT 91 and HIT 2000 studies, as follows:

Hearing – PTA	Dose Modification
< 16 dB at 1000-3000 Hz or ≤ 40 dB at 4000-8000 Hz	None
16-30 dB at 1000-3000 Hz or > 40 dB at 4000-8000 Hz	Substitute Carboplatin 400 mg/m  for Cisplatin
> 30 dB at 1000-3000 Hz	Omit any platinum

Grading for Audiometry is based on loss in both ears — Thus the grading (including that for modification of chemotherapy) is based on the Highest Grading i.e. the 'worst ear'.

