## 4.7.6 Audiology

High frequency hearing loss progressing to involve the speech frequency range (500-3,000 Hz) is a HIT-SIOP PNET 4 Protocol Version 3.0, 27th July 2010 (RG 10-034)

major toxicity of cisplatin. It is clear that the ototoxicity is dependent upon the cumulative dose of cisplatin, but other factors such as the dose per course and drug scheduling may be important. This effect is compounded by the effect of young age, the tumour itself, preceding cranial irradiation and dark eye colour 99. Of the 65 patients treated in CCG 9892, 21 (32.3 %) developed Grade 3 or 4 ototoxicity. In these patients, hearing loss occurred as early as the third cycle of CCNU, cisplatin, vincristine chemotherapy and as late as the seventh cycle. Ototoxicity was the principal reason for dose modification or curtailment of chemotherapy. By contrast, Grade 3 or 4 ototoxicity occurred in only 11 % of patients with medulloblastoma treated on the maintenance arm of the HIT 91 study, despite similar chemotherapy. The difference between the incidence of ototoxity noted in CCG 9892 and HIT 91 probably mainly reflects the difference in Cisplatin dose modification criteria used in these two studies.

Monitoring of hearing loss is a fundamental and mandatory part of this study. In PNET 4, the ototoxicity grading system devised for both HIT 91 and HIT 2000 will be used. Similarly, dose modification in PNET 4 will be that used in these two HIT Group studies. It is thus anticipated that ototoxicity associated with PNET 4 be significantly less than that reported from studies using Cisplatin containing maintenance therapy performed by the COG Group and elsewhere.

It is, however, appreciated that it is important to compare accurately the ototoxity following treatment according to the PNET 4 trial with other studies in which the Brock/CTC grading system  $^{100}$  ototoxity is generally used. In this respect, it is mandatory for patients entered into PNET 4 to have a pure tone audiogram performed at the end of treatment. Hearing loss at this time will be graded according to the Brock/CTC system and recorded either on the study Data Forms or, in the case of HIT Group patients, a hard copy of the audiogram will be sent the HIT Group National Data Centre.

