**Data to be collected:** Pure tone audiometry (PTA) will be undertaken before therapy and before every subsequent course of chemotherapy and graded according to the HIT scoring system (section 10.4.4). Chemotherapy will be modified on the basis of ototoxicity (section 10.4.4). Audiology will also be monitored as a late effect of treatment (section 10.4.4 and table in section 1.5) with the audiogram at end of treatment being graded according to the Brock/CTC system as described above.

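### In the cisplatin hearing table (Protocol 10.4.4), an *or* in the no-change row makes isolated high-frequency loss meet both the no-change and the carboplatin rows, and no precedence is stated

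*Protocol*

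**What the plan says.** The dose-modification table in section 10.4.4 of the Protocol has three rows, each keyed to the pure tone audiogram:

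- No modification: "< 16 dB at 1000-3000 Hz or ≤ 40 dB at 4000-8000 Hz".
- Carboplatin 400 mg/m² in place of cisplatin: "16-30 dB at 1000-3000 Hz or > 40 dB at 4000-8000 Hz".
- No platinum at all: "> 30 dB at 1000-3000 Hz".

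The sentence below the table says that grading, including the grading used to modify chemotherapy, "is based on the Highest Grading i.e. the 'worst ear". The same section also prints the HIT ototoxicity grades. These are defined only at or below 2000 Hz, for example "Grade 1: ≤ 15 dB at ≤ 2000 Hz".

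Section 4.7.6 makes this table operative: "Chemotherapy will be modified on the basis of ototoxicity (section 10.4.4". Section 10.2.1 requires audiology before each course. Section 4.7.6 also describes the typical cisplatin injury as "High frequency hearing loss progressing to involve the speech frequency range". It reports grade 3 or 4 ototoxicity of 32.3% in CCG 9892 and 11% in the HIT 91 maintenance arm, and says that this difference "probably mainly reflects the difference in Cisplatin dose modification criteria used in these two studies".

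**The concern.** The no-change row should describe an ear that is acceptable in both frequency bands. With *or* it describes an ear that is acceptable in either band. An ear with preserved speech frequencies and marked high-frequency loss therefore qualifies for no change through the first clause of that row, and for carboplatin through the second clause of the next.

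This is not a remote combination. Loss that starts at high frequencies and later reaches the speech range can pass through this state. It is also the stage at which a switch from cisplatin could still act before the speech range is involved.

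The table carries the modification criteria to which section 4.7.6 probably mainly credits the lower ototoxicity in HIT 91. Appendix B asks most national groups for a literal translation of the protocol, and has chemotherapy forms reviewed and deviations recorded. For this audiogram the printed text does not tell a reviewer which action is the deviation.

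**Working it through.** The plan gives no figure to reproduce. The check is of the table's logic.

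**Inputs.** The three rows of the section 10.4.4 table, with L the loss at 1000-3000 Hz and H the loss at 4000-8000 Hz:

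- No change if L < 16 **or** H ≤ 40.
- Carboplatin if 16 ≤ L ≤ 30 **or** H > 40.
- Omit platinum if L > 30.

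**Step 1: the audiogram at issue.** Take L = 10 dB and H = 50 dB in one ear. L < 16 is true, so the no-change row is met. H > 40 is true, so the carboplatin row is met. L > 30 is false. Two different instructions apply to the same ear.

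**Step 2: does anything else in the text decide it?**

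- The highest-grading sentence is glossed as the worst ear. It chooses between ears, not between two rows met by one ear.
- The HIT grades stop at 2000 Hz, so they do not register loss at 4000-8000 Hz.
- Section 4.7.6 only points back to section 10.4.4.
- Section 10.4 reserves individual responsibility and offers advice from the study chairman, but states no rule.

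**Step 3: which row is meant?** Suppose the milder row always won. An ear with L > 30 has either H ≤ 40, which meets the no-change row, or H > 40, which meets the carboplatin row. The omit-platinum row would then never operate. So the severer row must be meant, but this has to be inferred.

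**Step 4: does the correction work?** One value from each band (L = 10, 20, 35; H = 30, 50) gives these rows as printed, and then with *and* in the no-change row:

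- 10/30: no change; then no change.
- 10/50: no change and carboplatin; then carboplatin only.
- 20/30: no change and carboplatin; then carboplatin only.
- 20/50: carboplatin; then carboplatin.
- 35/30: no change and omit; then omit only.
- 35/50: carboplatin and omit; then still both.

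Changing the word removes every conflict that involves no change. The last combination is a conflict between the second and third rows that the *or* in row 1 does not cause. It needs a sentence saying that the most severe row applies.

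This list tests the wording and does not measure size. Only 10/50 is relied on. The combinations 20/30 and 35/30 run against the direction of progression in section 4.7.6.

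**Step 5: what is at stake per course.** Cisplatin 70 mg/m² (section 10.1) against carboplatin 400 mg/m² (section 10.4.4).

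**The case against.** The strongest reply is that only one reading is workable. The table is a ladder from no change to carboplatin to no platinum, and no clinician would give full cisplatin to a child with more than 30 dB loss in the speech range. On that view the *or* is a slip for *and*. In addition, a centre that applies the highest-grading principle broadly reaches carboplatin anyway, and the study chairman can be asked. This stands as to intent and keeps the point small. It does not make the wording right: the one sentence that could settle the matter is limited by its own gloss to the choice of ear.

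The reply on practical effect also largely stands. Planned recruitment ran to the end of 2005, with extension possible. This version is dated July 2010, when section 4.7.3.1 already cites emerging event-free survival results, so most dosing was probably complete. HIT Group centres use the amended HIT 2000 protocol (Appendix B), whose table is not shown.

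Some stronger readings are tempting but unsupported:

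- *The table licenses full-dose cisplatin.* It does not; it gives conflicting instructions.
- *The child in question is at most HIT Grade 1.* The HIT grades include frequencies below 1000 Hz, which this audiogram leaves open.
- *The wording raised ototoxicity, biased the arms or affected the stopping rule in section 13.7.* Nothing in the document shows this. Section 4.7.6 gives a direction of progression, with no thresholds and no frequency for this pattern.
- *The correction should also let a single tested band decide the dose.* The document gives no such rule, and one would allow full-dose cisplatin when the high frequencies are untested.

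**Conclusion.** The wording is wrong as printed, in an operative dosing rule. For less than 16 dB at 1000-3000 Hz with more than 40 dB at 4000-8000 Hz, the table gives both no change and carboplatin, and the protocol does not state which prevails. The intended answer, carboplatin, is evident from the structure of the table.

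Severity is minor. The consequence that can be stated is the choice of platinum agent at each affected course. How many courses or children are affected, and any cumulative dose, cannot be derived from the document. The point rests on the table being applied as printed and is shown only for centres using this text. The primary endpoint, significance levels and power are untouched.

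**What to change.** In section 10.4.4, change the no-change row to: *< 16 dB at 1000-3000 Hz AND ≤ 40 dB at 4000-8000 Hz: None*. Add below the table: *If the frequency bands meet different rows, the most severe row met, in the worse ear, applies.* Check both against the HIT source table before issue.

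The cost is one word and one sentence, with a notice to centres if any child is still receiving chemotherapy. If dosing is complete, one line in the ototoxicity report stating how the table was applied is enough.
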